While it is anticipated that not all mothers will agree to this sub-study, a sample size of 60 in each group will be targeted, with preference given to recruiting exposed pregnancies that represent the distribution of length of exposure.

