9.5 Study Size

An enrollment total of 75 in the exposed group and 150 in each of the 2 comparison groups after 10 years is anticipated. Given that these numbers assume the prevalence of exposure is sufficient to support recruitment of these numbers, the feasibility of achievement will be re-evaluated at each annual interim review of the data.

Based on previous experience with MotherToBaby/OTIS Pregnancy Studies, we estimate that subjects will be an average of 7-10 weeks post-LMP at the time of enrollment. Given this mean gestational timing at enrollment, the anticipated spontaneous abortion/stillbirth rate is 10%, the estimated elective abortion rate is 5%, and the estimated lost to follow-up rate is 5%. This results in an estimated 71 observable pregnancies of which 60 are estimated to result in live births in cohort 1 (exposed group), and an estimated 142 observable pregnancies of which 120 are estimated to result in live births in cohorts 2 and 3 (control groups).

Baseline rates of major structural **birth** defects, spontaneous abortion, premature delivery, and small for gestational age, as well as the standard deviation for mean birth weight of full-term infants were based on previous MotherToBaby/OTIS studies and on general population data (Table 3). With the sample size estimated above, at $\geq 80\%$ power, alpha of 0.05, two-tailed tests of significance (except as noted below for pattern of minor structural **birth** defects), and each comparison group independently compared to the exposed group, the minimum effect sizes detailed in Table 3 will be detectable.

With respect to the evaluation of minor malformations, the strength of this study design is in the ability to examine the data for a pattern of minor and/or major structural **birth** defects, given that the known human teratogens are typically associated with a pattern as opposed to isolated major **structural** birth defects. A baseline prevalence estimate of 1% has been used for a specific pattern of minor **structural birth** defects. The RR detectable with this sample size is 10.0. This represents a 10% birth prevalence of a specific pattern (ie, approximately 6 children in the exposed sample), which is comparable to the birth prevalence of a specific pattern in other known human teratogens of moderate risk such as the anticonvulsant medications.

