For the primary outcome, the study is powered to detect that the Evolocumab-Exposed group has a 3.8-fold (or greater) risk of all major **structural** birth defects combined relative to the risk in the primary comparison group. This level of risk for teratogenicity is below that observed for other, but not all, agents deemed teratogenic. Importantly, known human teratogens tend to be associated with increased risks for specific patterns of birth defects and are not associated with increased risks for any and all major **structural birth** defects. For this reason, the analysis of the primary outcome, combined with evidence of a cluster or pattern of defects, provides the best ability for evaluation of teratogenic risk.

Table 3. Sample Size and Power for a Specified Effect Size Based on Minimal Sample Size^a

Outcome	N in Cohort 1	N in Cohort 2 or 3	Baseline Rate	RR	Power ^b
Major structural birth defects ^c	71	142	4% ^d	3.8	84%
Specific pattern of 3 or more minor structural birth defects	60	120	1% ^e	10.0	71% ^f
Spontaneous abortion/stillbirth	71	142	10% ^g	2.5	88%
Preterm delivery	60	120	9% ^h	2.8	85%
SGA	60	120	10% ⁱ	2.6	80%
Small for age (postnatal growth deficiency)	46	108	10%	2.8	82%
Neurodevelopmental outcomes (Phase II)	40	40	--	0.5 SD ^j	80%
Inadequate immune response (via IgG tetanus antibody status)	60	120 ^k	20% ^l	2	82%

Definitions: Ig = immunoglobulin; RR = relative risk; SGA = small for gestational age.

^a Software used to calculate power and effect size: OpenEpi v3 (Dean et al, 2015).

^b Based on Fisher's Exact Test or chi-square, two-tailed, alpha 0.05, except for specific pattern of 3 or more minor anomalies as noted below.

^c Primary endpoint.

^d Baseline rate in comparison group based on 4.1% in statin exposed (Winterfeld et al, 2013).

^e Baseline rate in comparison group expected to be 0-1% based on no evidence of a pattern.

^f Based on one-tailed Fisher's Exact Test, alpha 0.05.

^g Baseline rate based on 13.6% in statin exposed (Winterfeld et al, 2013) and 4.4% (Chambers et al, 2013) (rate influenced by gestational time of enrollment).

^h Baseline rate based on 16.1% (Winterfeld et al, 2013) and 6.2% (Toleikyte et al, 2011).

ⁱ Baseline rate based on 5.0% for low birth weight defined as < 5th centile which translates to 10% for SGA defined as < 10th centile (Toleikyte et al, 2011).

^j Minimum detectable difference calculated for neurodevelopmental outcomes as a continuous variable (instead of RR for categorical variables).

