^k Estimating 60 infants per cohort.

^l Baseline rate based on Marshall et al (2010).

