9.7.2.5.2 Secondary Analysis

The following will comprise the secondary analyses:

1. Comparison of all secondary outcomes between the Specific Evolocumab-Exposed cohort and Comparison Group I
2. Comparison of the primary and all secondary outcomes between the Specific Evolocumab-Exposed cohort and Comparison Group II

The comparison of the prevalence of the total proportion of major structural **birth** defects between the Specific Evolocumab-Exposed cohort and Comparison Group II will be among all live births and, separately, among all pregnancies excluding those lost to follow-up. The comparison of the prevalence of ≥ 3 minor malformations between the Specific Evolocumab-Exposed cohort and each of the 2 comparison groups will be among children who receive the dysmorphological examination. The comparison of IgG-tetanus antibody status (test negative or indeterminate vs test positive) by group (Exposed, Comparison Group I, Comparison Group II) among those in the biological sample sub-study.

In each cohort we will separately calculate the proportion of all pregnancies ending in live birth, spontaneous abortion, stillbirth, elective termination, and lost to follow-up; crude comparisons will be made between cohorts.

The evaluation for a pattern of minor structural **birth** defects will be conducted using the following steps:

1. A comparison among groups of the proportion of infants with any 3 or more minor structural **birth** defects will be made without regard to pattern
2. Among infants with 3 or more minor **structural birth** defects, the Evolocumab-Exposed group will be examined for evidence of a specific pattern of 3 or more defects in any 2 or more children. If such a pattern is identified, Comparison Groups I and II will be evaluated for any evidence of the same pattern.

In each cohort among all live born infants we will separately calculate the proportion of premature delivery, small for gestational age on weight, length or head circumference, and rates of serious infections, hospitalizations, adverse vaccine reactions, and adverse neurodevelopmental outcomes; crude comparisons will be made between cohorts.

Mean birth weight, length and head circumference for full-term live born infants will be compared between cohorts. Postnatal growth parameters will be compared using the proportion of infants ≤ 10 th centile for sex and age with respect to weight, height, or head circumference.

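### Table 3's 82% power for the tetanus-antibody outcome rests on both comparison cohorts pooled (120); the planned one-cohort comparison (60 v 60) has about 60-68%

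*Protocol*

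**What the plan says.** Table 3 in Protocol 9.5 has one column for the exposed cohort and one headed "N in Cohort 2 or 3". The immune-response row enters 60 and 120, a 20% baseline rate of inadequate response, a relative risk of 2 and 82% power. A footnote attached to the 120 reads "Estimating 60 infants per cohort".

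The test behind the power column is given in another footnote: "Based on Fisher's Exact Test or chi-square, two-tailed, alpha 0.05, except for specific pattern of 3 or more minor anomalies as noted below". The text above the table says that its effect sizes are detectable at 80% power or more, with "each comparison group independently compared to the exposed group".

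Section 9.4.7 gives the sub-study's size: "a sample size of 60 in each group will be targeted".

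Section 9.7.2.5.2 lists two secondary comparisons: all secondary outcomes against Comparison Group I, and the primary and all secondary outcomes against Comparison Group II. For antibody status it describes a comparison "by group (Exposed, Comparison Group I, Comparison Group II) among those in the biological sample sub-study". It does not mention combining Groups I and II.

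**The concern.** The 82% appears to belong to a test that the plan does not run. If 60 infants are targeted per comparison cohort and each cohort is tested separately against the exposed group, the comparison arm of each test has 60 infants, not 120. Halving that arm at fixed rates lowers the power materially.

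The outcome matters more than its secondary rank suggests. Sections 7 and 7.1 cite humoral immune suppression in infant monkeys with another antibody of the class, and state that it was not assessed for evolocumab. The FDA requirement described in section 7 names outcomes related to humoral immune suppression. The tetanus antibody is the only biological measure of it in the registry. If its power is overstated, a null result will look more reassuring than it is.

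**Working it through.** **Inputs (Protocol 9.5, Table 3 and footnotes; 9.4.7)**
- Rates: comparison p0 = 0.20; exposed p1 = 2 × 0.20 = 0.40.
- Two-sided alpha 0.05, z = 1.960.
- Exposed n1 = 60. Comparison n0 = 120 as tabulated, or 60 for one cohort.

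**Where the 120 comes from.** The footnote and section 9.4.7 both give 60 per cohort, and 60 + 60 = 120. The table's other sub-sample row follows the opposite convention: section 9.4.5.2 plans 40 per group for face-to-face testing, and Table 3 enters 40 v 40, not 40 v 80.

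**Formula (pooled-variance normal approximation)**

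Power = Φ{[|p1 − p0| − z·√(p̄(1 − p̄)(1/n1 + 1/n0))] / √(p1(1 − p1)/n1 + p0(1 − p0)/n0)}, with p̄ = (n1p1 + n0p0)/(n1 + n0).

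**Step 1: reproduce the printed figure, 60 v 120**
- p̄ = (24 + 24)/180 = 0.2667
- Null standard error = √(0.1956 × 0.0250) = 0.0699; times 1.960 = 0.1370
- Alternative standard error = √(0.24/60 + 0.16/120) = 0.0730
- Power = Φ[(0.2000 − 0.1370)/0.0730] = Φ(0.862) = 80.6%

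**Step 2: the planned comparison, 60 v 60**
- p̄ = (24 + 12)/120 = 0.30
- Null standard error = √(0.21 × 0.0333) = 0.0837; times 1.960 = 0.1640
- Alternative standard error = √(0.24/60 + 0.16/60) = 0.0816
- Power = Φ[(0.2000 − 0.1640)/0.0816] = Φ(0.441) = 67.0%

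**Step 3: other two-sided methods.** The exact rows sum both binomial distributions over every table with p ≤ 0.05.

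| Method | 60 v 120 | 60 v 60 |
|---|---|---|
| Pooled normal | 80.6% | 67.0% |
| Chi-square, exact enumeration | 81.3% | 68.4% |
| Unpooled normal | 78.2% | 68.8% |
| Continuity-corrected normal | 75.5% | 59.4% |
| Fisher's exact test, exact enumeration | 77.7% | 60.0% |

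The printed 82% is approached only with 120 comparison infants. No method brings 60 v 60 above 69%.

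**Step 4: what 60 v 60 can detect.** By the pooled normal formula, power is 78.1% at a relative risk of 2.15 and 81.3% at 2.20. By Fisher's test it is 79.1% at 2.25 and 82.1% at 2.30. So 80% power needs a relative risk of about 2.2 to 2.3, that is, 44% to 46% inadequate response among the exposed.

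**Step 5: the size needed to keep relative risk 2 at 80% power with equal groups.** n = [1.960·√(2 × 0.30 × 0.70) + 0.842·√(0.24 + 0.16)]²/0.20² = (1.270 + 0.532)²/0.04 = 81.2, so 82 per group. With continuity correction it is 91.

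**The case against.** **The 82% is about right for the numbers in its row.** This stands. The fault is an inconsistency between the row's sample size and the planned test, not a slip in computing power.

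**The footnote discloses the 60 per cohort, and the entry for Amendment 1 in section 5 describes the comparison infants as a combined 120.** A pooled comparison may therefore have been intended. If so, it never reached section 9.7.2.5.2, and section 9.5 says the reverse. Writing in a pooled comparison would be a legitimate repair. The footnote does not tell the reader that the 82% belongs to a pooled test.

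**Sixty is a target, not a cap.** Section 9.4.7 offers the sub-study in all three cohorts, and section 9.5 expects 120 live births in each comparison cohort. More than 60 might be sampled, but 60 is the only planning figure given and the footnote to this row uses it.

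**The antibody sentence in 9.7.2.5.2 is incomplete and could describe one three-group test.** With 60 per group at 40%, 20% and 20%, a two-degree-of-freedom chi-square test has about 73% power, still below 82%. The numbered list in the same section points to separate comparisons.

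**The outcome is secondary, and section 9.9 concedes limited power.** Both are true, and 95% confidence intervals are planned. That moderates the consequence but does not make the printed figure right.

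**The 20% baseline is itself in doubt.** Section 9.4.7 expects nearly all children in every group to test positive. If the baseline were 1%, 2% or 5% (assumed values), power at relative risk 2 with 60 v 60 would be about 7%, 9% or 18%. This separate point also stands: any restated power is conditional on the 20%.

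**Conclusion.** The concern holds. On Table 3's own inputs (20% baseline, relative risk 2, two-sided 0.05), exposed infants against one comparison cohort of 60 give 60.0% power by Fisher's test and 68.4% by chi-square, against the printed 82%: an overstatement of about 14 to 22 percentage points. Comparing like with like, moving from 120 to 60 costs 12.9 points by chi-square (81.3 − 68.4) and 17.7 by Fisher (77.7 − 60.0). The claim in 9.5 of at least 80% power is therefore not met for this outcome.

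The conclusion rests on 60 infants per cohort being achieved and on separate comparisons with Groups I and II, both as the protocol states them. It does not depend on the choice of two-sided test. Power for the primary endpoint is untouched.

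**What to change.** In Table 3, replace 120 with 60 in the immune-response row. Then either keep relative risk 2 and state power of about 60% (Fisher) to 68% (chi-square), or state the relative risk detectable with 80% power as about 2.2 to 2.3. Name the test used, and mark this row as an exception to the 80% statement in 9.5 if relative risk 2 is kept.

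Alternatively, if a pooled comparison is wanted, write it into 9.7.2.5.2 for this outcome, justify combining a disease-matched group with a group without the disease, and label the 120 as Groups I and II combined. The separate comparisons would still need their own, lower power stated.

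While the row is open, reconcile the 20% baseline with the expectation in 9.4.7 of near-universal positivity, and state that the power is conditional on the baseline chosen.

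The first option costs one table row and the sentence in 9.5 that refers to it, with no change to recruitment, sampling or conduct. The stated figure becomes less favourable. Restoring 80% power at relative risk 2 by enlarging the sub-study would instead need about 82 infants per group in an equal design, more than the 60 exposed live births that 9.5 expects.

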9.6 Data Management

Interview, medical record, examination, neurodevelopmental and biological sample sub-study data will be recorded on hard copies of forms and these records will be retained in the Research Center. Data from these forms will be extracted and entered into a customized database located in the Research Center. The data will be extracted and entered by trained study personnel with extensive experience with this type of information. Entries will be periodically reviewed for logical errors, and a random subset of intake and outcome forms will be double-checked for data entry accuracy. Access to the database will be controlled by password. Hard copies of patient files and subject signed consent forms will be kept in a locked cabinet under the supervision of the study investigators.

9.7 Data Analysis

9.7.1 Planned Analyses

9.7.1.1 Interim Analysis/Analyses

No formal interim analyses are planned. However, the appropriate regulatory authorities will receive:

- Annual reports of analyses performed during the study for the advisory board.
- A feasibility/futility report 3 years after study commencement, and annually thereafter, summarizing the number of subjects enrolled, any exposure to evolocumab, and describing primary and secondary outcome data.

9.7.1.2 Primary Analysis

The primary analysis will be conducted at the end of the study. The objective of the primary analysis is to compare the rates of the primary and secondary outcomes in the evolocumab-exposed and diseased comparison group.

9.7.1.3 Final Analysis

The final analysis will be conducted at the end of the study observation period (currently scheduled to occur 15 years after study commencement) or when the study is determined to have been completed based on other criteria (eg, FDA agreement).

9.7.2 Planned Method of Analysis

9.7.2.1 General Considerations

The analysis of the cohort dataset will be hypothesis testing. The analysis of the exposed case series will be descriptive only. Significance testing at the alpha level of 0.05 will be utilized for the cohort analysis as well as 95% confidence intervals for rate ratios. Due to the small sample size, no adjustment for multiple testing is planned.

9.7.2.2 Demographic and Baseline Characteristics

Demographic and baseline characteristics will be summarized by cohort. Discrete variables will be summarized using numbers and percentages; continuous variables will be summarized using means and SD or medians and IQR, as appropriate. When making comparisons between cohorts, discrete variables will be compared using chi-square tests. If $\geq 25\%$ of categories have expected counts less than 5, Fisher's Exact tests will be used. Continuous variables will be analyzed using analysis of variance (ANOVA).

9.7.2.3 Missing or Incomplete Data and Lost to Follow-up

Pregnancies enrolled in the cohort study for which outcome information is unobtainable within 1 year after the estimated date of delivery are considered lost to follow-up. It is possible that outcomes among pregnancies lost to follow-up could differ from those with documented outcomes. Because of differences in follow-up and reporting patterns, it is currently not possible to assess with any certainty what impact the potential biases the lost to follow-up may have on any analysis of the cohort study. Should lost to follow-up numbers be substantial, however, efforts at comparing some of the characteristics of each group will be made in an attempt to address this potential source of bias. However, the OTIS Research Center prior experience has been that lost to follow-up is extremely low, typically < 5%.

9.7.2.4 Descriptive Analysis

Descriptive results will be presented in each annual report.

Results for the fourth group (Evolocumab-Exposed Case Series) will be summarized separately from other cohorts. All analyses of this cohort will be descriptive and no comparisons to the other cohorts will be made. These cases constitute an exposure series, thus line listings of major malformations, pattern of minor malformations, serious infections, hospitalizations, and any neonatal deaths will be summarized along with tabulations of the frequencies of events by category of report: reasons for exclusion, timing of exposure, and indication for use of the medication. Although select, and likely biased, collection of exposure and outcome information in this group is important for providing additional evidence on the safety of evolocumab use during pregnancy.

9.7.2.4.1 Description of Study Enrollment

Outcome	Analysis Subset
Major Structural Birth Defect Among Live Births	All pregnancies ending in at least 1 live born infant
Major Structural Birth Defects Among All Pregnancies Excluding Lost to Follow-Up	All pregnancies excluding lost to follow-up
Spontaneous Abortion	Pregnancies enrolled prior to 20 weeks' gestation
Stillbirth	Pregnancies enrolled excluding lost to follow-up
Preterm Delivery	Pregnancies enrolled prior to 37 completed weeks' gestation, excluding pregnancies ending in twin or higher order multiple births
Minor Structural Birth Defects	Live born infants who have received the dysmorphology examination
Small for Gestational Age Infants	Live born infants excluding twin or higher order multiple births
Breastfeeding	Pregnancies ending in at least 1 live born infant
Postnatal Growth	Live born infants followed up to 1 year postpartum, excluding twin or higher order multiple births
Serious or Opportunistic Infections	Live born infants followed up to 1 year postpartum
Immune Function	Live born infants who received the tetanus titer testing
Response to vaccines	Live born infants who received at least one vaccine
Neurodevelopment	Live born infants for whom developmental screening questionnaires were completed or face-to-face testing was completed

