9.3.2.2 Secondary Outcomes

9.3.2.2.1 Pregnancy Outcomes

- Rate of spontaneous abortion where spontaneous abortion is defined as non-deliberate fetal death which occurs prior to 19 completed weeks post-LMP
- Rate of elective abortion where elective abortion is defined as deliberate termination of pregnancy at any time in gestation
- Rate of stillbirth where stillbirth is defined as non-deliberate fetal death anytime in gestation at or after 19 completed weeks post-LMP
- Rate of premature delivery where premature delivery is defined as live birth prior to 37.0 weeks gestation as counted from LMP (or ultrasound adjusted date)

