Among the subset of live born infants who participate in the IgG-tetanus antibody assessment at 6-12 months of age, adequacy of immune response will be compared between groups.

Among mothers who give birth to live born infants, the proportion who breastfeed in the first 6 weeks post-delivery will be compared; also among those who breastfeed, the proportion who breastfed exclusively during the first 2 weeks of life.

At the end of the study or as deemed appropriate in consultation with the Scientific Advisory Board, unadjusted and adjusted comparisons between cohorts will be made. Potential confounders will be examined, and adjusted estimates of exposure effects (along with 95% confidence intervals) will be made using Cox proportional hazards, logistic regression, or linear regression techniques as appropriate. Propensity score methods will be considered for adjusted analyses when more than 1 confounder is identified.

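### Spontaneous abortion: the analysis subset and the crude denominator do not match the 19-week definition, and the crude comparison is open to bias if cohorts enrol at different weeks

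*Protocol*

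**What the plan says.** Section 9.3.2.2.1 of the protocol defines spontaneous abortion as "non-deliberate fetal death which occurs prior to 19 completed weeks post-LMP" and stillbirth as "non-deliberate fetal death anytime in gestation at or after 19 completed weeks post-LMP". The two definitions meet at 19 weeks without overlap.

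The subset table in 9.7.2.4.1 sets the spontaneous-abortion population as "Pregnancies enrolled prior to 20 weeks" of gestation. That row does not exclude pregnancies lost to follow-up; the stillbirth row does.

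Section 9.7.2.5.2 calculates, in each cohort, "the proportion of all pregnancies ending in live birth, spontaneous abortion, stillbirth, elective termination, and lost to follow-up; crude comparisons will be made" between cohorts. It sets no limit on week of enrolment, and loss to follow-up is one of the categories. Section 9.4.2 and footnote a of Table 1 give interview schedules for women who enrol from 19 weeks to below 30 weeks, at 30 weeks and later, so such women are expected.

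Later in 9.7.2.5.2 the protocol adds that "unadjusted and adjusted comparisons between cohorts will be made", using "Cox proportional hazards, logistic regression, or linear regression techniques as appropriate". No outcome is assigned to a model.

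Footnote g of Table 3 (section 9.5) gives baseline rates of 13.6% and 4.4% from two sources and notes "rate influenced by gestational time of enrollment".

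**The concern.** A woman who enrols at 19 completed weeks or later cannot have a spontaneous abortion as defined, yet she counts as a pregnancy without one. The subset table admits one such week. The all-pregnancies denominator admits every such woman, together with women whose outcome is unknown. The two denominators also differ from each other, so the protocol does not say which proportion is the result.

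The second issue is left truncation. A woman is observed only from enrolment, and the earlier she enters, the more of the risk period she contributes. A crude proportion treats entry at 7 weeks and at 14 weeks alike. If exposed and comparison women enrol at different average weeks, the crude relative risk departs from 1 with no drug effect.

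Nothing in the design fixes this balance. Comparison Group I is frequency-matched on disease indication (9.1), not on gestational week, and 9.2.4 marks matching as not applicable. Stratification on enrolment timing (9.7.2.6, 9.9) is planned for birth defects only. At stake is a false signal, or a masked one, on a secondary safety outcome.

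**Working it through.** **Inputs from the protocol.** The event window closes at 19 completed weeks (9.3.2.2.1). Average enrolment is expected at 7 to 10 weeks after the last menstrual period, with no figure by cohort (9.5). The anticipated rate of spontaneous abortion and stillbirth combined is 10% (9.5). Table 3 gives a detectable relative risk of 2.5 for that combined outcome, with 71 versus 142 pregnancies.

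**The plan's own figure.** Table 3 states 88% power for that row. A two-sided pooled chi-square test with 25% versus 10% and 71 versus 142 gives 80.1%; a one-sided test gives 87.1%. The 88% is thus not reproduced with the stated two-tailed test. That is a separate matter and nothing below depends on it. The 2.5 serves only as a yardstick.

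**Step 1: women not at risk in the denominator.** Let f_E and f_C be the shares of exposed and comparison women who enrol at 19 weeks or later. With no drug effect and otherwise equal entry,

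crude RR = (1 − f_E) / (1 − f_C).

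Equal shares cancel in the ratio, although both rates are understated. If only the comparison cohort has such women, RR = 1 / (1 − f_C):

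| f_C | crude RR |
|---|---|
| 1% | 1.01 |
| 2% | 1.02 |
| 5% | 1.05 |
| 10% | 1.11 |

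For the 19-versus-20-week mismatch, f is the share entering in that single week. For the all-pregnancies denominator, f is the share entering at any week from 19 on; the formula is the same.

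**Step 2: entry week, all women in a cohort entering together.** The risk remaining at entry week e is

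R(e) = 1 − product over w = e to 18 of (1 − h(w)), with h(w) = c × q^(w − 7).

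The protocol gives no hazard shape, so q is an assumption. The constant c is set so that the average of R(8) and R(9) is 10%, which applies the protocol's combined loss rate to spontaneous abortion alone.

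| Assumed weekly hazard | c | R(7) | R(10) | RR, exposed 7 vs comparison 10 | RR, reversed |
|---|---|---|---|---|---|
| constant (q = 1) | 0.010 | 11.35% | 8.64% | 1.31 | 0.76 |
| falls 20% a week (q = 0.8) | 0.032 | 14.03% | 6.91% | 2.03 | 0.49 |
| falls 30% a week (q = 0.7) | 0.054 | 16.49% | 5.78% | 2.85 | 0.35 |

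The weekly hazards are identical in both cohorts in every row, so the true ratio is 1.00. An analysis by gestational week with delayed entry targets that value. If both cohorts enter at the same week, the crude RR is also 1.00.

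**Step 3: entry spread over weeks.** Assume a continuous hazard that halves every three weeks, scaled to 13.6% risk from week 7. Entry is normal with SD 2 weeks, truncated to weeks 6 to 18. The reference cohort (location 10, mean entry 10.1 weeks) has a crude risk of 7.0%.

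| Location | Mean entry after truncation | Crude risk | RR vs 7.0% |
|---|---|---|---|
| 7 | 8.0 weeks | 11.2% | 1.59 |
| 8 | 8.6 weeks | 10.0% | 1.42 |
| 9 | 9.3 weeks | 8.5% | 1.21 |

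The ratios use unrounded risks. A difference in mean entry of roughly one to two weeks thus gives a null RR of about 1.2 to 1.6.

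**The case against.** The crude proportion is not the only planned comparison. Section 9.7.2.5.2 also promises adjusted estimates and names Cox regression, for which time to pregnancy loss is a natural use, and 9.9 speaks of hazards of late first-trimester and early second-trimester loss. Time scale, delayed entry and censoring are details that a protocol commonly leaves to the analysis plan, which is not shown. Comparison women are described as similarly ascertained through the same services (9.1), and the documents do not say that exposed women enrol earlier. With average entry at 7 to 10 weeks, few women should enter in week 19.

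Much of this stands. A reader might infer that the relative risk is biased. The documents do not support that, because bias needs a difference in entry timing that they neither state nor rule out. A reader might also take the 13.6% and 4.4% in footnote g as the size of the timing effect. The footnote says only that timing influences the rate. The figures come from different populations, one a study of statin-exposed pregnancies and the other a study of pandemic influenza vaccine, and they support a combined abortion and stillbirth row. Their 3.1-fold ratio (13.6 / 4.4) cannot be read as an effect of enrolment week.

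What does not fall away is the conflict among 9.3.2.2.1, 9.7.2.4.1 and 9.7.2.5.2, which the protocol itself states and an analysis plan would inherit. Nor does adjustment in general terms answer left truncation: Cox is not tied to this outcome, and covariate adjustment alone does not correct the risk set.

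**Conclusion.** The point holds in limited form. The definition, the analysis subset and the crude denominator conflict, and women who cannot have the event are counted as non-events. The crude comparison is open to bias in either direction if entry timing differs between cohorts.

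The 19-versus-20-week mismatch alone is minor, at about 1.01 to 1.11 even when 1 to 10% of one cohort only enters in that week. The entry-week effect can be material against the relative risk of 2.5 in Table 3: about 1.3 to 2.9 for week 7 versus week 10, or about 1.2 to 1.6 with spread entry. These figures illustrate what could happen. They rest on assumed hazard shapes and on assumed differences in entry, and they vanish if the cohorts enrol at the same weeks. The outcome is secondary, so this should be corrected but does not threaten the primary comparison.

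**What to change.** - In 9.7.2.4.1, set the spontaneous-abortion subset to pregnancies enrolled before 19 completed weeks.
- In 9.7.2.5.2, use that same denominator for the between-cohort comparison of spontaneous abortion, and state how pregnancies lost to follow-up are handled.
- Name the comparison of spontaneous abortion as a Cox or Kaplan-Meier analysis on gestational age, with delayed entry at enrolment and follow-up to 19 completed weeks. State how elective terminations end follow-up.
- Keep the crude proportions of pregnancy outcomes as description.

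The cost is a few lines of protocol wording and routine code. Gestational dating (9.3.1) and outcome dates (9.4.3) are already collected, and week of enrolment already drives the interview schedule (9.4.2), so no new data are needed.
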